8.2.1.3. Safety

The primary analysis set for safety analyses is defined as the safety analysis set, which will include all participants who (1) are randomized into the study and (2) have received at least 1 dose of study treatment. All data collected up to 30 days after participants permanently discontinue their study treatment will be included in the safety summaries, unless specified otherwise. Participants will be grouped according to the treatment they actually received.

8.3. Data Handling Conventions

HIV-1 RNA results of ‘No HIV-1 RNA detected’ and “<20 cp/mL HIV-1 RNA Detected” will be imputed as 19 copies/mL for analysis purposes.

Laboratory data that are continuous in nature, but are less than the lower limit of quantitation or above the upper limit of quantitation, will be imputed to the value of the lower or upper limit plus or minus one significant digit, respectively (eg, if the result of a continuous laboratory test is < 20, a value of 19 will be assigned).

Missing data can have an impact upon the interpretation of the trial data. In general, values for missing data will not be imputed. However, a missing pre-treatment laboratory result would be treated as normal (ie, no toxicity grade) for the laboratory abnormality summary.

All available data for participants that do not complete the study will be included in data listings.

8.4. Demographic Data and Baseline Characteristics

Demographic and baseline characteristics will be summarized using standard descriptive methods, including sample size, mean, SD, median, Q1, Q3, minimum, and maximum for continuous variables, and frequency and percentages for categorical variables.

Demographic data will include sex, race, ethnicity, age, sexual orientation and gender identity.

Baseline characteristics will include body weight, height, eGFR, HIV-1 infection, and enrollment distribution will be summarized.

For categorical demographic and baseline characteristics, the Cochran–Mantel–Haenszel test will be used to compare treatment groups. For continuous demographic and baseline characteristics, the Wilcoxon rank sum test will be used to compare treatment groups.

8.5. Efficacy Analysis

8.5.1. Primary Analysis

The primary analysis will consist of a non-inferiority test of switching to FDC of B/F/TAF versus SBR, with respect to the proportion of participants with HIV-1 RNA \geq 50 copies/mL at Week 24, as defined by the US FDA-defined snapshot algorithm. The primary analysis of the efficacy endpoint will be based on the FAS.

8.5.1.1. US FDA-defined Snapshot Algorithm

All HIV-1 RNA data collected on-treatment (ie, including data collected up to 1 day after the last dose date of study drug) will be used in the snapshot algorithm. Virologic outcome will be defined as the following categories:

- **HIV-1 RNA < 50 copies/mL:** this includes participants who have the last available on-treatment HIV-1 RNA < 50 copies/mL in the Week 24 analysis window
- **HIV-1 RNA ≥ 50 copies/mL:** this includes participants
 - a) Who have the last available on-treatment HIV-1 RNA ≥ 50 copies/mL in the Week 24 analysis window, or
 - b) Who do not have on-treatment HIV-1 RNA data in the Week 24 analysis window and
 1. Who discontinue study treatment prior to or in the Week 24 analysis window due to lack of efficacy, or
 2. Who discontinue study treatment prior to or in the Week 24 analysis window due to reason other than lack of efficacy and have the last available on-treatment HIV-1 RNA ≥ 50 copies/mL
- **No Virologic Data in the Week 24 Analysis Window:** this includes participants who do not have on-treatment HIV-1 RNA data in the Week 24 analysis window because of the following:
 - a) Discontinuation of study treatment prior to or in the Week 24 analysis window due to reasons other than lack of efficacy and the last available on-treatment HIV-1 RNA < 50 copies/mL, or
 - b) Missing data during the window but on study treatment

8.5.1.2. Analysis of Primary Efficacy Endpoint

The null hypothesis is that the proportion of participants achieving HIV-1 RNA < 50 copies/mL (as defined by the US FDA-defined snapshot algorithm) at Week 24 in B/F/TAF is at least 6% lower than the response rate in SBR; the alternative hypothesis is that the response rate in B/F/TAF is less than 6% lower than that in SBR.

Non-inferiority will be assessed using the conventional confidence interval (CI) approach. The point estimate of treatment difference (B/F/TAF – SBR) and the associated 2-sided 95% CI will be constructed based on the exact method.

It will be concluded that FDC of B/F/TAF is non-inferior to SBR if the upper bound of the 2-sided 95% CI of the difference between treatment groups [B/F/TAF – SBR] in the percentage of participants with HIV-1 RNA \geq 50 copies/mL is less than 6% (i.e., a margin of 6% is applied to non-inferiority assessment).

If non-inferiority of B/F/TAF to SBR is established, the upper bound of the 95% CI will be compared to 0; if the upper bound of the 95% CI is less than 0, superiority of B/F/TAF over SBR will be established.

8.5.2. Secondary Analyses

The proportion of participants with HIV-1 RNA < 50 copies/mL at Weeks 24 and 48, and the proportion of participants with HIV-1 RNA \geq 50 copies/mL at Week 48 as defined by the US FDA-defined snapshot algorithm will also be summarized.

The changes from baseline in CD4+ cell count at Weeks 24 and 48 will be summarized by treatment using descriptive statistics. The differences between treatment groups at Week 24 and the associated 95% CIs will be constructed using an Analysis of Variance (ANOVA) model, including treatment (B/F/TAF vs. SBR) as a fixed effect in the model.

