Efficacy:	
The primary efficacy endpoint is:
 
• The proportion of participants with HIV-1 RNA \geq 50 copies/mL at Week 24 as defined by the US FDA-defined snapshot algorithm 
The secondary efficacy endpoints are:
 
• The proportion of participants with HIV-1 RNA \geq 50 copies/mL at Week 48 as defined by the US FDA-defined snapshot algorithm• The proportion of participants with HIV-1 RNA $<$ 50 copies/mL at Week 24 and 48 as defined by the US FDA-defined snapshot algorithm• The change from baseline in CD4+ cell count at Weeks 24 and 48.

Patient reported
outcomes:

HIV Symptoms Distress Module Index will be administered at Day 1, Weeks 4, 24, 28 (SBR only) and 48. HIV Treatment Satisfaction Questionnaire Status (HIV-TSQs) will be administered at Day 1 and HIV Treatment Satisfaction Questionnaire Change (HIV-TSQc) will be administered at Week 4 and Week 24. Visual Analogue Scale (VAS) Adherence Questionnaire will be administered at Day 1 and at all visits up to (and including) Week 24 for participants in Treatment Group 2 (SBR) only.

Statistical Methods:

The primary analysis will consist of a non-inferiority test of switching to FDC of B/F/TAF versus SBR, with respect to the proportion of participants with HIV-1 RNA ≥ 50 copies/mL at Week 24, as defined by the US FDA-defined snapshot algorithm. It will be concluded that FDC of B/F/TAF is non-inferior to SBR if the upper bound of the 2-sided 95% confidence interval (CI) of the difference between treatment groups [B/F/TAF – SBR] in the percentage of participants with HIV-1 RNA ≥ 50 copies/mL is less than 6% (i.e., a margin of 6% is applied to non-inferiority assessment). The 2-sided 95% CIs will be constructed based on the exact method.

The proportion of participants with HIV-1 RNA < 50 copies/mL at Weeks 24 and 48, and the proportion of participants with HIV-1 RNA ≥ 50 copies/mL at Week 48 as defined by the US FDA-defined snapshot algorithm will also be summarized. The 95% CIs at Week 24 will be constructed in the same manner as described for the primary efficacy endpoint.

The change from baseline in CD4+ cell count at Weeks 24 and 48 will be summarized by treatment using descriptive statistics. The differences and the associated 95% CIs at Week 24 will be constructed using an Analysis of Variance (ANOVA) model, including treatment (B/F/TAF vs. SBR).

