- Includes patients who discontinued due to AE or death at any time point from Day 1 through the time window if this resulted in no virologic data on treatment during the specified window.
- Includes patients who discontinued for reasons other than an AE, death or lack or loss of efficacy, e.g., withdrew consent, loss to follow-up, etc.

B/F/TAF FDC was noninferior in achieving HIV-1 RNA < 50 copies/mL at Week 48 when compared to ABC/DTG/3TC and DTG+FTC/TAF, respectively. Treatment outcomes were similar across subgroups by age, sex, race, baseline viral load, and baseline CD4+ cell count.

In Studies 1489 and 1490, the mean increase from baseline in CD4+ count at Week 48 was 207, 229, and 201 cells per mm³ in the pooled B/F/TAF FDC, ABC/DTG/3TC, and DTG+FTC/TAF groups, respectively.

Bone Mineral Density:

In Study 1489, bone mineral density (BMD) change from baseline to Week 48 was assessed by dual-energy X-ray absorptiometry (DXA). In patients who had both baseline and Week 48 hip and lumbar spine BMD measurements (N = 257 and 267 in the B/F/TAF FDC group and N = 270 and 274 in the ABC/DTG/3TC group, for hip and lumbar spine, respectively), mean percentage changes in BMD were similar in the B/F/TAF FDC group compared to the ABC/DTG/3TC group for hip (-0.8% vs. -1.0%) and lumbar spine (-0.8% vs. -0.6%).

Virologically Suppressed Patients

In Study 1844, the efficacy and safety of switching from a regimen of DTG + ABC/3TC or ABC/DTG/3TC to B/F/TAF FDC were evaluated in a randomized, double-blind study of virologically-suppressed (HIV-1 RNA < 50 copies/mL) HIV-1 infected adults (N = 563). Patients must have been stably suppressed (HIV-1 RNA < 50 copies/mL) on their baseline regimen for at least 3 months prior to study entry. Patients were randomized in a 1:1 ratio to either switch to B/F/TAF FDC at baseline (N = 282), or stay on their baseline antiretroviral regimen (N = 281). Patients had a mean age of 45 years (range 20-71), 89% were male, 73% were White, and 22% were Black. 17% of patients identified as Hispanic/Latino. The mean baseline CD4+ cell count was 723 cells/mm³ (range 124-2444).

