In Study 1878, the efficacy and safety of switching from either ABC/3TC or FTC/TDF (200/300 mg) plus ATV or DRV (boosted by either COBI or RTV) to B/F/TAF FDC were evaluated in a randomized, open-label study of virologically-suppressed HIV-1 infected adults (N = 577). Patients must have been stably suppressed on their baseline regimen for at least 6 months and INSTI naïve prior to study entry. Patients were randomized in a 1:1 ratio to either switch to B/F/TAF FDC (N = 290), or stay on their baseline antiretroviral regimen (N = 287). Patients had a mean age of 46 years (range 20-79), 83% were male, 66% were White, and 26% were Black. 19% of patients identified as Hispanic/Latino. The mean baseline CD4+ cell count was 663 cells/mm³ (range 62-2582). Patients were stratified by prior treatment regimen. At screening, 15% of patients were receiving ABC/3TC plus ATV or DRV (boosted by either COBI or RTV) and 85% of patients were receiving FTC/TDF plus ATV or DRV (boosted by either COBI or RTV).

Treatment outcomes of Studies 1844 and 1878 through Week 48 are presented in [Table 1-2](#).

Table 1-2. Virologic Outcomes of Studies 1844 and 1878 at Week 48^a

	Study 1844		Study 1878	
	B/F/TAF FDC (N = 282)	ABC/DTG/3TC (N = 281)	B/F/TAF FDC (N = 290)	Baseline ATV- or DRV-based regimen (N = 287)
HIV RNA < 50 copies/mL	94%	95%	92%	89%
Treatment Difference (95% CI)	-1.4% (-5.5% to 2.6%)		3.2% (-1.6% to 8.2%)	
HIV-1 RNA ≥ 50 copies/mL ^b	1%	<1%	2%	2%
Treatment Difference (95% CI)	0.7% (-1.0% to 2.8%)		0.0% (-2.5% to 2.5%)	
No Virologic Data at Week 48 Window	5%	5%	6%	9%
Discontinued Study Drug Due to AE or Death and Last Available HIV-1 RNA < 50 copies/mL	2%	1%	1%	1%
Discontinued Study Drug Due to Other Reasons and Last Available HIV-1 RNA <50 copies/mL ^c	2%	3%	3%	7%
Missing Data During Window but on Study Drug	2%	1%	2%	2%

- a. Week 48 window was between Day 295 and 378 (inclusive).
- b. Includes patients who had ≥ 50 copies/mL in the Week 48 window; patients who discontinued early due to lack or loss of efficacy; patients who discontinued for reasons other than lack or loss of efficacy and at the time of discontinuation had a viral value of ≥ 50 copies/mL.
- c. Includes patients who discontinued for reasons other than an AE, death or lack or loss of efficacy, e.g., withdrew consent loss to follow-up, etc.

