In Study 1844, at Week 48, switching to B/F/TAF FDC was noninferior to remaining on ABC/DTG/3TC. The percentages of patients with HIV-1 RNA ≥ 50 copies/mL and who maintained HIV-1 RNA < 50 copies/mL were similar between the B/F/TAF FDC and ABC/DTG/3TC groups. The mean change from baseline in CD4+ count at Week 48 was -31 cells per mm³ in patients who switched to B/F/TAF FDC and 4 cells per mm³ in patients who stayed on ABC/DTG/3TC.

In Study 1878, at Week 48, switching to B/F/TAF FDC was noninferior to remaining on an ATV- or DRV-based regimen. The percentages of patients with HIV-1 RNA ≥ 50 copies/mL and who maintained HIV-1 RNA < 50 copies/mL were similar between the B/F/TAF FDC and ATV- or DRV-based regimen groups. The mean change from baseline in CD4+ count at Week 48 was 25 cells per mm³ in patients who switched to B/F/TAF FDC and 0 cells per mm³ in patients who stayed on their baseline regimen.

Bone Mineral Density:

In Study 1844, BMD change from baseline to Week 48 was assessed by DXA. In patients who had both baseline and Week 48 hip and lumbar spine BMD measurements (N = 229 and 233 in the B/F/TAF FDC group and N = 242 and 244 in the ABC/DTG/3TC group, for hip and lumbar spine, respectively), mean percentage increases in BMD were similar in the B/F/TAF FDC group compared to the ABC/DTG/3TC group for hip (0.2% vs. 0.3%) and lumbar spine (0.7% vs. 0.4%).

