6.9.1. Blood Samples

- Blood sample collection for the following laboratory analyses will be performed at every study visit, unless otherwise specified:
 - Serum pregnancy test (all female participants). If the test is positive, the participant will not be enrolled (**Screening only**).
 - FSH test: Required for female participants who are <54 years old and have stopped menstruating for ≥ 12 months but do not have documentation of ovarian hormonal failure (**Screening only**)

— Chemistry profile: alkaline phosphatase, AST, ALT, total bilirubin, direct and indirect bilirubin, total protein, albumin, CPK, bicarbonate, blood urea nitrogen (BUN), chloride, creatinine, glucose, potassium, sodium, amylase, and Cystatin C

- Calcium, phosphorus, magnesium, amylase (reflex lipase testing is performed in participants with total amylase > 1.5 × ULN) (**Screening and Day 1 only**)

- Cystatin C (**Day 1 only**)

— Metabolic assessments: Fasting (no food or drinks, except water, at least 8 hours prior to blood collection) glucose and lipid panel (total cholesterol, HDL, direct LDL, and triglycerides) collected at **Day 1, Weeks 24, 48, and 72**.

- If the participant has not fasted prior to the visit, the visit may proceed, but the participant must return within 72 hours in a fasted state to draw blood for the metabolic assessments

— eGFR according to the Cockcroft-Gault formula:

Male:
$$\frac{(140 - \text{age in years}) \times (\text{wt in kg})}{72 \times (\text{serum creatinine in mg/dL})} = \text{creatinine clearance (CLcr)} \text{ (mL/min)}$$

$$\frac{(140 - \text{age in years}) \times (\text{wt in kg})}{72 \times (\text{serum creatinine in umol/L}) \times 0.6786} = \text{CLcr (mL/sec)}$$

Female:
$$\frac{(140 - \text{age in years}) \times (\text{wt in kg}) \times 0.85}{72 \times (\text{serum creatinine in mg/dL})} = \text{CLcr (mL/min)}$$

$$\frac{(140 - \text{age in years}) \times (\text{wt in kg}) \times 0.85}{72 \times (\text{serum creatinine in umol/L}) \times 0.6786} = \text{CLcr (mL/sec)}$$

— Hematology profile: complete blood count (CBC) with differential and platelet count

— CD4+ cell count and percentage (**Screening, Day 1, Weeks 24, 48, and 72, 30 Day Follow-up and ESDD**)

— Plasma HIV-1 RNA. Any subsequent HIV-1 genotype and phenotype testing will be performed as described in Sections [6.13.1](#) and [6.13.2](#).

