- n Chemistry profile: alkaline phosphatase, AST, ALT, total bilirubin, direct and indirect bilirubin, total protein, albumin, CPK, bicarbonate, BUN, calcium, chloride, creatinine, glucose, phosphorus, magnesium, potassium, sodium, amylase, and Cystatin C. After Day 1, calcium, phosphorous, magnesium, and amylase (reflex lipase testing is performed in participants with total amylase $> 1.5 \times$ ULN) will not be collected. Analyses of glucose will be done as part of the fasting metabolic assessments, and not as part of the chemistry profile at Day 1, Weeks 24, 48, and 72. Cystatin C will only be collected at Day 1.
- o Metabolic Assessments will be performed at Day 1, Weeks 24, 48, and 72. Fasting (no food or drinks, except water, at least 8 hours prior to blood collection) glucose and lipid panel (total cholesterol, HDL, direct LDL, triglycerides). If the participant has not fasted prior to the visit, the visit may proceed, but the participant must return within 72 hours in a fasted state to draw blood for the metabolic assessments.
- p CBC with differential and platelet count.
- q HIV-1 genotype and phenotype testing for participants with confirmed virologic failure and HIV-1 RNA >200 copies/mL. Following virologic rebound, participants will be asked to return to the clinic (2-3 weeks later) prior to the next scheduled visit or at the next scheduled study visit for a HIV-1 RNA and HIV-1 resistance analysis (reverse transcriptase, protease, and integrase genotype and phenotype) blood draw. Based on the results of this testing, participants should be managed according to the Virologic Rebound Schema.
- r CD4+ Cell Count and Percentage to be collected at Screening and Day 1, and every 24 weeks thereafter, at Weeks 24, 48, and 72, in addition to the 30 Day Follow-up Visit and ESDD.
- s HBV blood panel will be performed at Screening and Week 48: HBsAg, HBsAb, HBcAb.
- t **For participants who are HBV co-infected (defined in Section 6.9.1):** The following HBV Blood panel will be conducted by the central laboratory: HBsAb, HBsAg (qualitative and quantitative), and HBeAg (if negative, reflex HBeAb).
For participants who are NOT HBV co-infected: The following HBV Blood panel will be conducted by the central laboratory: HBsAb, HBcAb, and HBsAg. Participants who are HBsAg or HBcAb positive will have a reflex test for HBV DNA (viral load).
- u **For participants who are HBV co-infected:** Plasma HBV DNA will be collected at Day 1, Week 24, Week 48 and ESDD.

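### The Week 24 comparison of CD4+ change leaves out baseline CD4+; adding it would usually narrow the 95% CI by a few percent at no data cost

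*Protocol*

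**What the plan says.** Change from baseline in CD4+ count at Weeks 24 and 48 is a secondary efficacy endpoint (Protocol 3.1 and 8.1.3). Protocol 8.5.2 summarizes it descriptively and, at Week 24 only, gives a between-arm difference and 95% CI from an "Analysis of Variance (ANOVA) model, including treatment (B/F/TAF vs. SBR) as a fixed effect in the model". The synopsis names the same model. Neither place mentions baseline CD4+ or the randomization stratum.

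The baseline value is available. Appendix 2, footnote r, has "CD4+ Cell Count and Percentage to be collected at Screening and Day 1, and every 24 weeks thereafter", and Protocol 6.9.1 agrees.

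The supplied SAP covers the final analysis only. Its section 1 refers the primary and secondary efficacy analyses to a Week 48 SAP, which is not supplied. Section 6.2.1 records that these analyses have been performed and will not be repeated. Section 6.4 plans no change from the protocol's efficacy analyses, but this SAP runs no CD4+ comparison.

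**The concern.** An ANOVA on change subtracts the baseline count and so fixes its slope at 1. An ANCOVA estimates that slope. Unless the true slope is 1, the change score carries baseline variation that could have been removed. The interval is then wider than it needs to be, and a chance baseline difference between arms moves the estimate. Randomization is stratified on third-agent class only (Protocol 5.1), so balance in CD4+ is left to chance.

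The stake is how well a secondary comparison can be read. For scale, Protocol 1.2.3.4 reports mean CD4+ changes at Week 48 in two earlier switch studies of −31 versus 4 and 25 versus 0 cells/mm³. The between-arm differences are −31 − 4 = −35 and 25 − 0 = +25, which is not far from the half-width to be expected here.

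**Working it through.** The plan gives no SD, correlation or precision for CD4+, so it has no figure of its own to reproduce. The stated 89% power concerns the primary endpoint and is not affected.

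**Inputs.** From the documents: 320 and 160 participants, 95% CI. Assumed: baseline SD s, Week 24 SD k·s, and correlation ρ between baseline and Week 24.

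**Variances**, each multiplied by (1/320 + 1/160):
- change score: s²(1 + k² − 2ρk)
- ANCOVA: s²k²(1 − ρ²)

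The width ratio is √[k²(1 − ρ²)/(1 + k² − 2ρk)]. At k = 1 it reduces to √[(1 + ρ)/2]. It does not depend on s or on the 2:1 allocation. At ρ = 0.7, for example, √(1.7/2) = 0.922.

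**Narrowing of the CI:**

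| Week 24 SD / baseline SD | ρ = 0.7 | ρ = 0.8 | ρ = 0.9 |
|---|---|---|---|
| 0.9 | 13.3% | 11.2% | 10.0% |
| 1.0 | 7.8% | 5.1% | 2.5% |
| 1.1 | 4.0% | 1.6% | 0.0% |

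At equal SDs, ρ = 0.5 gives 13.4%. The gain vanishes where ρk = 1. Allowing for the degree of freedom spent, the equal-SD row becomes 7.7%, 5.0% and 2.4%. As a sample-size equivalent, 1/ratio² − 1 is about 18%, 11% and 5% more participants.

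**Simulation check** (6,000 trials per cell, 320 versus 160, SD 250). Mean narrowing was 13.2%, 11.2%, 9.9% at k = 0.9; 7.7%, 5.0%, 2.4% at k = 1; and 3.9%, 1.5%, −0.1% at k = 1.1. Coverage of both models was 0.945 to 0.958 (Monte Carlo SE 0.003), so both intervals are valid.

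**Half-width** = t × SD × √(1/320 + 1/160), with t = 1.965 and a square-root term of 0.0968. With an assumed SD of 250 and k = 1:
- ρ = 0.7: SD of change 250√0.6 = 193.6, ANCOVA residual SD 250√0.51 = 178.5; half-width 36.8 falls to 34.0
- ρ = 0.8: 30.1 falls to 28.5
- ρ = 0.9: 21.3 falls to 20.7 cells/µL

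At ρ = 0.8, SD 200 gives 24.1 to 22.8 and SD 400 gives 48.1 to 45.7, a gain of about 1.2 to 2.5 cells/µL.

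The upper SD is a rough guess. Dividing the baseline ranges in Protocol 1.2.3.4 by the expected normal range gives (2444 − 124)/6.145 = 378 for n = 563 and (2582 − 62)/6.160 = 409 for n = 577. These are probably too high if the counts are right-skewed.

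**Chance imbalance.** A baseline difference D shifts the change-score estimate by −(1 − ρk)D. One standard error of D is 250 × 0.0968 = 24.2 cells/µL. At k = 1 the shift is then 7.3, 4.8 or 2.4 cells/µL for ρ = 0.7, 0.8, 0.9, against about 0 for ANCOVA. That is 7% (2.4/35) to 29% (7.3/25) of the differences in the earlier studies. In simulation the slopes on D were within 0.011 of −(1 − ρk) for ANOVA and of 0 for ANCOVA.

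**The case against.** The strongest objection is that the model actually run cannot be seen. The protocol gives an outline, its wording does not exclude further terms, and the Week 48 SAP may have added the covariate. This stands. The supplied documents show a covariate missing from the protocol text, not from the analysis as performed.

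It is also fair that this is a refinement. CD4+ change has no margin, test or success rule, the saving at SD 250 is 0.6 to 2.8 cells/µL, and with the analysis done any adjusted result is post hoc.

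Two points limit how the size may be presented. First, the imbalance shift is not a second harm on top of the wider interval. The change-score variance equals the ANCOVA variance plus (1 − ρk)²s², so the shift is that extra term seen conditionally, and the ANOVA interval already allows for it. Second, the comparison with −35 and +25 depends on the assumed SD of 250 and sets Week 48 results against a Week 24 interval. At SDs of 378 and 409, with ρ = 0.8 and k = 1, the half-widths would be about 45 and 49, above both differences.

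None of this removes the point that a covariate already collected is left unused in the stated model.

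**Conclusion.** The point holds as an inexpensive improvement and not as an error. The stated ANOVA is valid. Adding baseline CD4+ would narrow the Week 24 interval by about 2.5% to 8% if the two SDs are equal and ρ is 0.7 to 0.9, and by 0% to 13% if the Week 24 SD may be 10% above or below baseline. The correlation, SD ratio and SD are all assumptions. The half-widths also assume all 480 planned participants contribute; the percentages do not depend on that. No trial decision turns on the result, and the point lapses if the Week 48 SAP already adjusts.

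**What to change.** The plan should have specified, for the Week 24 difference in CD4+ change, an ANCOVA with treatment as a factor and baseline CD4+ count as a covariate. Because the analysis has been run, the prespecified text should not be rewritten or the ANOVA demoted. Check the Week 48 SAP first. If it adjusts for baseline CD4+, nothing more is needed. If it does not, keep the ANOVA as the prespecified result and report the ANCOVA estimate and 95% CI beside it, labelled supplementary (post hoc).

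A stratum term is optional; it probably adds little, and its effect was not computed. If one is used, take the third-agent class from IWRS, which gives each participant one class, and state this as a departure from SAP 3.3, which prefers the clinical database where the two disagree. Under SAP Appendix 6, item 9, a participant entering in violation with two third agents is counted in both classes in summaries, which would not work as a model factor.

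The cost is one document check and at most one extra table row, with no new data. The drawback is that the row is not prespecified.
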